Most hemodialysis patients receive therapy sessions thrice weekly, typically for 12 hours per week. The stability of sessions varies, with an average of 20% becoming unstable—most commonly from intradialytic hypotension (IDH); this affects half of all hemodialysis patients.⁴⁵⁻⁴⁸ IDH may prompt cramping, dizziness, vomiting, fainting, and fatigue.^{40, 49, 50} Serious unstable sessions lead to hospitalization or even death on days in which dialysis was received⁵¹⁻⁵³. The chief cause of unstable hemodialysis sessions is rapid removal of large volumes of fluid; this is driven by both patient-level and facility-level factors.⁴⁸ Indeed, there are wide facility-level variations in IDH rates after controlling for patient characteristics,⁴⁸ 20% of the variation in IDH is predicted at the patient level.⁵⁴

Hemodialysis session instability is associated with repetitive and cumulative cardiovascular and other organ system injury.⁵⁵⁻⁵⁷ Large volumes of fluid (3 liters or more) may be removed at higher than desired ultrafiltration rates during a typical HD session due in part to high interdialytic weight gains. In the face of pre-existing diminished cardiovascular reserves, this may result in HD instability and repeated myocardial hypoperfusion with resultant wall-motion abnormalities, an event called “myocardial stunning”.⁵⁵⁻⁵⁷ Emerging evidence shows it may be responsible for injury resulting from hypoperfusion in other microcirculatory beds, including in the central nervous system (e.g., repetitive neurological injury leading to cognitive dysfunction).⁵⁸

The most common form of hemodialysis session instability, IDH, predicts low quality of life, hospitalization and mortality.^{47, 59} Our team⁶⁰ and others^{17, 18} have shown that a care process directly linkable to IDH onset, the ultrafiltration rate (i.e. rate of fluid removal) greater than 10 ml/h/kg bodyweight, is linked to elevated mortality risk. Of note, the FMCNA UFR goal is <13 ml/kg/hr. We have also shown that the thrice-weekly schedule paradigm is associated with significantly higher mortality earlier in the week, potentially due to the long interdialytic interval over the weekend, which leads to a greater need for fluid removal early in the week.⁶¹ Negative symptoms may result in session shortening by patients or providers.⁶² A national survey found that 90% of hemodialysis providers had witnessed sessions stopped due to patient status in the three months prior.⁶³

2.1.4 IMPORTANCE OF THE STUDY:

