A final type of attrition may be the possibility of missing data due to patients not completing the self-reported quality of life (KDQOL) survey or the patient symptom question regarding recovery time. For example, some participants may refuse to answer certain questions or may miss follow-up surveys. Where possible, we will note reasons for missing data by triangulating data sources to determine whether a patient has moved to another facility, or in accordance with two of our outcomes, been hospitalized or die. Although every effort will be made to collect these data, some missing surveys are still likely, particularly among those in ill health. We do not expect missing surveys to be associated with study arm, but missingness itself can be analyzed for treatment differences as a tertiary outcome measure. The sample in each cross-section will include living patients only, so death will not be a problem as it would be in a longitudinal QOL study. We believe that this approach, along with our conservative assumptions regarding sessions needed as described previously, will largely prevent missing data for our primary outcome, as well as two secondary ones. Death will be tracked as an outcome, although the trial is not powered to assess this as a primary outcome. Data on subjects who leave the study site, will be used until their time of departure from the study. In other words, we will not track data for patients after they transfer to a non-study facility.

We will compare the characteristics of those with missing data to those without missing data, to test whether characteristics are similar between the groups. In addition to complete case analyses, we will use state-of-the-art statistical methods such as likelihood approaches and multiple imputation to deal with missing data.¹⁶⁰ These sensitivity analyses will assess the robustness of the results to missing data.

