16% in the intervention group. It is assumed that a minimum of 60 hemodialysis patients will be observed for at least 60 dialysis sessions and the outcome will be the proportion of unstable sessions, which we treat as a continuous variable. These proportions among patients in a facility are assumed to be normally distributed with mean 0.20 in the control group and mean between 0.16 and 0.17 in the intervention group (a difference, d , of 0.034 to 0.043), with standard deviation (SD, or 'sigma') assumed to be in the range 0.08 to 0.10. We conservatively assume $n=60$ patients per facility, i.e., a total of $60 \times 20 = 1,200$ patients. The power calculation is robust to changes in number of patients (m), as the calculation of K (number of clusters) only increases by ~ 1 if m is increased to 90. The intraclass correlation coefficient for hemodialysis facilities is assumed to be 0.10. A significance level of 0.05 was assumed in all calculations. Table 5 gives the statistical power to detect a given difference (D , 0.034-0.043), with sigma values of 0.08 and 0.10, and number of clusters (dialysis units, k) per treatment group of 10 (20 facilities total).

Table 5 shows that detecting a difference of ~ 0.03 (i.e., 20% versus 17% of sessions unstable) with 80% power is only feasible with a SD (sigma) of 0.08 or less. If the standard deviation is as large as 0.10, we can detect a difference of 0.043 (i.e., 20% vs. 16%) with 81% power. Put another way, if the smallest variance estimate is correct ($\sigma=0.08$), we have 91% power to detect a 4% difference, and 80% power to detect a 3% difference.

Table 5 - The power is shown to detect a difference in IDH rates (D) between groups assuming 3 possible standard deviations (sigma). The minimum number of facilities (K) is also shown, illustrating some flexibility to accommodate drop-out. Bolded cells show power $\geq 80\%$.						
D	0.034	0.034		0.040	0.043	
Sigma	0.08	0.10		0.08	0.10	
K	10	10		10	10	
Power	80%	61%		91%	81%	

II. Secondary Outcomes

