11.4 FINAL ANALYSIS PLAN

Aim 1. Test and conduct a cluster-randomized controlled trial (CRCT) to compare the effects of the above HD facility-level interventions on the primary outcome of dialysis

session stability over an intervention period of 24 weeks and a post-intervention follow-up period of 12 weeks.

Preliminary data analysis. We will compare the four randomized groups to assess covariate balance on participant characteristics, such as demographics. This analysis will test for potential selection bias that might lead to confounding of study results. If study arms are found to be imbalanced on baseline characteristics, in addition to those specified in the analyses below, these characteristics will be included in the regression models as a sensitivity analysis.

Analysis of Primary Outcome. For Aim 1, the outcome is a dichotomous measure of HD stability, where an unstable session is defined as the dialysis session stability, where an unstable session is defined as SBP falling below 100 when the starting SBP was ≥ 100 . This outcome will be collected through digital records for all HD sessions of all patients at each facility during the study period. The analysis will be done in two ways. First, as a continuous variable, as described in the power analysis. Using individuals with a minimum of 60 dialysis sessions, the proportion of unstable sessions will be computed. Linear mixed models will be employed to compare individuals in facilities in the two treatment arms to individuals in the non-intervention facilities. Random effects for facility clustering will be accounted for using the MIXED procedure in SAS. As a sensitivity analysis, dialysis session stability will also be examined as a yes/no variable and analysis will be carried out on the longitudinal dataset using logistic regression with a random effect for both patients and facilities, using the GLIMMIX procedure in SAS. The random effects will model the correlations among the measurements at each level. This analysis will use data from all patients, not just those with at least 60 dialysis sessions.

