effect. (Further discussed in the heterogeneity of effects section). Although the study is not powered to detect even moderate interaction effects, it is possible that a strong interaction could be detected, and such an effect would be of interest.

The primary results will be based on the treatment effects tested in the initial models described for cluster-randomized trials with pre-planned covariates. Intent-to-treat analyses will be carried out, so that any deviations from the randomized interventions will not be taken into account in the primary test of treatment effects. Additionally, we will conduct as-treated analyses for the peer mentoring intervention whereby only patients who received peer mentoring are compared to patients in the other treatment arms, with adjustment for the same factors as in the intent-to-treat analyses. The small number of facilities (20) will preclude post-hoc adjustment for facility non-compliance with the interventions.

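### The primary model analyses only patients with at least 60 dialysis sessions, so inclusion depends on survival, retention and attendance after randomisation

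*Combined protocol and SAP*

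**What the plan says.** Section 11.4 (Analysis of Primary Outcome), repeated in Section 11.2, specifies two analyses. The first treats each patient's proportion of unstable sessions as continuous in a linear mixed model with a random facility effect: "Using individuals with a minimum of 60 dialysis sessions, the proportion of unstable sessions will be computed". The second, labelled a sensitivity analysis, is a session-level logistic model fitted with GLIMMIX: "This analysis will use data from all patients, not just those with at least 60 dialysis sessions".

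Section 11.4 then says: "The primary results will be based on the treatment effects tested in the initial models described for cluster-randomized trials with pre-planned covariates". It adds: "Intent-to-treat analyses will be carried out, so that any deviations from the randomized interventions will not be taken into account".

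The figure of 60 first appears as a planning assumption for power in Section 11.2: "It is assumed that a minimum of 60 hemodialysis patients will be observed for at least 60 dialysis sessions".

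Aim 1 refers to "session stability over an intervention period of 24 weeks and a post-intervention follow-up period of 12 weeks", but neither section says over which weeks the 60 sessions are counted. The interdialytic weight gain, recovery-time and symptom-burden outcomes in Section 11.2 do name the 24-week intervention period. On patients who leave, Section 5.4.3 says: "Data on subjects who leave the study site, will be used until their time of departure from the study".

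**The concern.** A planning assumption has become an inclusion rule for the primary result, and whether a patient meets it is known only after the facility has been randomised and the intervention has begun. Death, transfer, change of modality, late entry and missed sessions all decide who is analysed.

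This would matter little if those events had nothing to do with IDH or with arm. The protocol argues otherwise. Section 2.2.1 holds that dialysis adherence predicts session stability. Section 14.3, in justifying the consent waiver, ties IDH to regular attendance and warns against losing the patients who have IDH most often. Both interventions could also alter session counts. Attendance is a target of Patient Education Session 1, and staff training parts 2 and 3 (Section 2.1.1) ask staff to discuss adding a session or a treatment day with the physician. If the arms differ in which IDH-prone patients reach 60 sessions, the comparison is no longer between the groups as randomised. Even without such a difference, the result describes longer-staying, better-attending patients rather than everyone enrolled.

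**Working it through.** **1. Which window?** Nothing states it for the primary outcome, but two places point to 24 weeks. The feasibility metric in Section 10.1 (VI) asks for 3,600 sessions per pilot clinic during the pilot intervention period, and 3,600 = 60 patients x 60 sessions. Section 11.4 treats the 12-week follow-up as a separate maintenance analysis. Both are indirect, since one is a pilot metric and the other a secondary analysis.

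**2. What 60 sessions requires.** Section 2.1.3: "Most hemodialysis patients receive therapy sessions thrice weekly". At that rate 60 sessions take 60/3 = 20 full weeks.

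| Window | Sessions available | Share needed | Latest entry that can still qualify |
|---|---|---|---|
| 24 weeks | 72 | 60/72 = 83% | end of week 4 |
| 36 weeks | 108 | 60/108 = 56% | end of week 16 |

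Section 4.1 (VI) enrols new patients until 8 weeks before the intervention ends, that is, until about week 16. Under the 24-week reading, entrants between weeks 4 and 16 generally cannot qualify. The 12-week baseline supplies at most 36 sessions at this rate, so even a window that included it would need at least 60 - 36 = 24 sessions after the intervention starts.

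**3. Share unable to qualify even with perfect attendance.** Input: 15-20% turnover over the 11-month (48-week) study (Section 5.4.1), with a steady rate assumed. Let t be 0.15 or 0.20.

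- Present at the start but gone within 20 weeks: 1 - (1 - t)^(20/48) = 6.5% or 8.9%. This is the 36-week answer, about 80-105 of 1,200.
- For 24 weeks, add entrants from weeks 4 to 16, t x 12/48 = 3.75% or 5.0%, and divide by everyone enrolled, 1 + t x 16/48: (0.0655 + 0.0375)/1.050 = 9.8%, or (0.0888 + 0.0500)/1.067 = 13.0%. That is about 120-155 of 1,200.
- Late entry is 0.0375/0.1030 or 0.0500/0.1388 of the 24-week numerator, about 36%.

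Missed sessions come on top. The documents give no attendance rate. If misses were independent (an assumption), the chance of at least 60 of 72 would be 0.975, 0.72 and 0.30 at 90%, 85% and 80% attendance. For at least 60 of 108 it is about 1 at all three.

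**4. Does the filter buy power?** The variance of a facility mean is 0.1 x SD^2 + 0.9 x SD^2/m, and SE = sqrt(2 x variance/10). With SD 0.08 and m = 60, the variance is 0.00064 + 0.00576/60 = 0.000736 and SE = 0.01213. Power for 0.034 (two-sided 0.05, normal) is 80.0%, which matches Table 5. The other three cells give 61.1%, 90.9% and 80.9% against the stated 61%, 91% and 81%.

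Now let a fraction f of the 60 fall below 60 sessions. The filtered analysis has m = 60(1 - f). The unweighted all-patient analysis replaces 0.00576 by 0.00576 + f x 0.00998. Here 0.00998 is the mean extra binomial variance, 0.16 x (1/n - 1/60), for session counts n spread evenly over 1 to 59 (assumed).

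| f | All patients, unweighted | Filtered |
|---|---|---|
| 10% | 79.1% | 79.5% (m = 54) |
| 20% | 78.3% | 78.8% (m = 48) |

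The filter gains at most half a point.

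**The case against.** The restriction is disclosed, and an all-patient analysis is prespecified beside it. That stands as a real safeguard. But it changes the population, the model and the effect scale together, so a disagreement between the two analyses could not be traced to the restriction.

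The plan also says, in Section 5.4.3 and again in Section 11.4, that its conservative session assumption should largely prevent missing primary data, and it promises likelihood methods and multiple imputation. This may mean that patients below 60 sessions are to be treated as missing. The text does not say so, and it presents those methods as sensitivity analyses.

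Four stronger readings are tempting and are not supported:

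- A reader might infer that the window is wholly open, with baseline sessions as a live option. The indirect evidence favours 24 weeks, and nothing suggests pooling baseline into a treatment-effect proportion.
- A reader might infer that the bias must count against the patient intervention because it targets attendance. Provider-arm staff are trained to raise extra sessions, which could also lift the counts of IDH-prone patients, so the direction is open.
- A reader might take the 10-13% as loss through death, transfer and non-attendance. Over a third is late entry, for which the documents give no reason to expect a difference by arm.
- A reader might say that the filter breaches the plan's intent-to-treat rule. As the plan words that rule, it concerns deviations from the assigned intervention, and the filter reassigns nobody. The tension is with analysing everyone enrolled and with using leavers' data until departure, which the primary model does not do for anyone who leaves before 60 sessions.

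**Conclusion.** The concern holds as a should-fix point. The primary result rests on a subset defined by events after randomisation, with a counting window that has to be inferred. On the protocol's turnover figure at a steady rate and thrice-weekly dialysis, about 10-13% of patients cannot enter the primary model under the 24-week reading, or 7-9% under a 36-week one, before any missed sessions. The thresholds are not strict for every patient, because the protocol says only that most dialyse three times a week. The size and direction of any bias in the treatment comparison cannot be derived from the documents, and any figure for it would rest wholly on assumed attendance and on an assumed link with IDH. The restriction has no compensating benefit in power.

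**What to change.** In Sections 11.2 and 11.4:

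1. State the counting window for the primary outcome and reconcile it with Aim 1's 24 weeks plus 12 weeks of follow-up. Say whether the 60 counts all sessions or only those with starting SBP of at least 100.
2. Make the primary analysis the same linear mixed model on all enrolled patients with at least one eligible session (starting SBP of at least 100) in that window. Use weights or a variance that allows for session count; Section 11.4 already contemplates such weights in the maintenance analysis.
3. Keep the 60-session subset in the same model as a sensitivity analysis, so that the effect of the restriction can be seen on its own. Retain the GLIMMIX analysis.
4. Report by arm how many patients fall below 60 sessions and why: death, transfer, late entry or missed sessions.

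The cost is SAP wording, since the data are already collected. The drawback is noise from short stays: at a proportion of 0.2 the sampling SE is 0.40 for one session, 0.12 for 12 and 0.05 for 60, which fits the normality assumption in Section 11.2 less well. That is the reason for allowing for session count rather than giving a one-session patient full weight. Weights that depend on session count still lean towards longer-staying patients, so the unweighted estimate should be shown beside the weighted one.

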Précis:	
This project is a pragmatic, cluster-randomized comparative effectiveness trial through education of patients and healthcare providers, and the use of a checklist to heighten attention to patient clinical factors. The study compares a healthcare provider-focused to a patient-focused intervention in 20 hemodialysis facilities that are all part of the same parent organization. Facilities will be randomized in a 2x2 factorial design, such that 5 sites will receive the patient education intervention, 5 sites will receive the facility training and checklist intervention, 5 sites will receive both interventions, and 5 sites will receive neither intervention. The CRCT will compare the effectiveness of the two interventions for improving the primary outcome of HD session stability, operationalized as intradialytic hypotension (IDH). This outcome will be monitored for 12 weeks prior to the intervention, for 24 weeks during the intervention period and for 12 weeks after the intervention period (Aim 1). The interventions will also be assessed in terms of their effects on secondary outcomes, including patient symptoms, fluid adherence, dialysis adherence, quality of life, hospitalizations and mortality (Aim 2). We will also identify factors associated with successful implementation of the Dialysafe interventions, and ways in which implementation may influence intervention effectiveness (Aim 3).

Objectives:	
We will compare two interventions to improve the cardiovascular/hemodynamic stability of HD care by pursuing the following specific aims:
 
● Aim 1 Conduct a cluster-randomized controlled trial (CRCT) to test and compare the effects of the above HD facility-level interventions on the primary outcome of dialysis session stability over an intervention period of 24 weeks and a post-intervention follow-up period of 12 weeks.● Aim 2 Test and compare the effects of the two HD facility-level interventions on secondary patient-centered clinical outcomes, including: patient symptoms, fluid adherence, dialysis adherence, quality of life, hospitalizations and mortality over the same timeframe.

- **Aim 3** Identify factors associated with successful implementation of the interventions, and ways in which implementation may influence intervention effectiveness.

[figure not shown]
Population:	1,200-1,440 patients, ages 21 and older, receiving in-center hemodialysis for chronic kidney disease
Phase:	IV
Number of Sites:	20

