3 OBJECTIVES

3.1 STUDY OBJECTIVES

We will compare two interventions to improve the cardiovascular/hemodynamic stability of HD care by pursuing the following specific aims:

- **Aim 1** Conduct a cluster-randomized controlled trial (CRCT) to test and compare the effects of the above HD facility-level interventions on the primary outcome of dialysis session stability over an intervention period of 24 weeks and a post-intervention follow-up period of 12 weeks.
- **Aim 2** Test and compare the effects of the two HD facility-level interventions on secondary patient-centered clinical outcomes, including: patient symptoms, fluid adherence, dialysis adherence, quality of life, hospitalizations and mortality over the same timeframe.
- **Aim 3** Identify factors associated with successful implementation of the interventions, and ways in which implementation may influence intervention effectiveness.

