7.2 ENROLLMENT/BASELINE

Details for the opt-out process can be found in the attached *Opt out process* document. The initial patient opt out process is planned to last up to 4 weeks, with patients being given 1 week to opt out after receiving the Patient Information Sheet (PIS). All clinics will have the 12-week baseline data collected retrospectively. The estimated timeline for the staggered rollout of the study for the 20 clinics will begin with the first clinic opt out process in January 2023, and the last clinic post intervention data collection period ending in October 2024. We do not anticipate monitoring for changes in facility or participant eligibility during the course of the study.

The Patient Information Sheet (PIS) will be distributed to all patients during a hemodialysis session by an FMCNA study facility staff member. The Staff member will use wording similar to this script when giving the information sheet to the patients.

"This sheet tells you about a study from the University of Michigan that Fresenius Medical Care and our Medical Director have approved for our clinic. The goal of the study is to help patients feel better by taking steps to prevent low blood pressures during dialysis. All patients in the clinic will be in the study. However, after you review the details on this sheet you can choose to opt out of the use of your data by letting me know or by calling the toll-free number on the last page. You can also get more information about the study by calling the toll-free number."

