For the above analyses, the variables of primary interest are the main effects of the interventions. *Session-level* covariate adjustment will include: (1) weekday of session, (2) dialysis session shift, (3) average session blood flow rate; (4) average session dialysate flow rate, and (5) dialysate composition (sodium, potassium, magnesium). *Patient-level* covariate adjustment will comprise: (1) patient demographics (age, race, ethnicity, sex, employment, literacy, education level, language spoken); (2) time since first dialysis; (3) cause of ESRD, (4) treatment history; (5) total transplants; (6) vascular access type; (7) patient laboratory data (serum phosphorous, dialysis adequacy, anemia management (hemoglobin), iron indices (serum ferritin, serum iron), mineral metabolism indices (calcium, phosphate, PTH)); (8) comorbidity index; (9) individual comorbidities and comorbidities in combination, including COVID-19; (10) patient's heart rate variability (based on variability in heart rate (HR) during dialysis session (difference between the highest and lowest heart rates, standard deviation of the heart rate measures, the square root of the mean squared differences of successive heart rate measures); (11) patient medications (prescriptions medications administered outside of center or in-center (including ESA prescription, iron, antibiotics and vitamin D analog), and non-in-center prescriptions). Patient data will be censored while they are at COVID-19 isolation facilities. Regression diagnostics will be used to assess model fit. Checks for functional form of continuous adjustment covariates will be carried out and any transformations will be implemented prior to adding the intervention variables to the model.

Three secondary analyses are planned for this Aim. The first will test the treatment effects in a similar model but adding adjustment for any covariates found to be unbalanced between treatment groups in preliminary analyses. This has the ability to further adjust for important confounders of treatment effects, but because it will use data-driven covariate decisions that are subject to analysis bias, it will be interpreted with caution. The next secondary analysis will test the interaction between the two interventions to detect a possible synergistic or antagonistic

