In both Aims 1 and 2, the primary results will be based on the treatment effects tested in the initial models described for CRCTs with pre-planned covariates. Depending on the specific outcome, covariate adjustment for these analyses will include: (1) patient demographics (age, race, ethnicity, sex, employment, literacy, education level, language spoken), (2) time since first dialysis, (3) cause of ESRD, (4) treatment history, (5) total transplants, (6) vascular access type, (7) patient laboratory data (serum phosphorous, dialysis adequacy, anemia management (hemoglobin), iron indices (ferritin, serum Iron), mineral metabolism indices (calcium, phosphate, PTH)); (8) comorbidity index; (9) individual comorbidities and comorbidities in combination, including COVID-19; (10) patient's heart rate variability for the whole session or up until IDH occurs (if IDH occurs) (based on variability in heart rate (HR) during dialysis session (Difference between the highest and lowest heart rates, standard deviation of the heart rate measures, the square root of the mean squared differences of successive heart rate measures)); and (11) patient medications (prescriptions medications administered outside of center or in-center (including ESA prescription, iron, antibiotics and vitamin D analog)). Intent-to-treat analyses will be carried out, which means that any deviations from the randomized interventions will not be taken into account in the primary test of treatment effects. Additionally, we will conduct as-treated analyses for the peer mentoring intervention whereby only patients who received peer mentoring are compared to patients in the other treatment arms, with adjustment for the same factors as in the intent-to-treat analyses. The small number of facilities (20) will preclude post-hoc adjustment for facility non-compliance with the interventions.

Heterogeneity of Treatment Effect Analyses (Moderation). As with the primary outcome analyses, the following potential moderators will be assessed: 1) patient demographics, including age, race, ethnicity, literacy, and education level; (2) comorbidities; and (3) heart rate variability.

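### The primary model omits the 12-week baseline IDH rate already collected at every facility; adjusting for it adds precision if the facility-level correlation exceeds about 0.25

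*Combined protocol and SAP*

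**What the plan says.** The Précis says of IDH: "This outcome will be monitored for 12 weeks prior to the intervention". Section 7.2 adds: "All clinics will have the 12-week baseline data collected retrospectively". So a pre-intervention value of the primary outcome exists for every facility.

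Section 11.4 lists five session-level and eleven patient-level covariates for Aim 1. The patient-level list contains "2) time since first dialysis; (3) cause of ESRD, (4) treatment history; (5) total transplants; (6) vascular access type" and goes on to laboratory data, comorbidity, heart rate variability and medications. The Aim 2 text repeats the patient-level list. Neither list names earlier IDH, and neither contains a facility-level covariate. These lists define the main result. For Aim 1: "The primary results will be based on the treatment effects tested in the initial models described for cluster-randomized trials with pre-planned covariates". For Aims 1 and 2 together: "the primary results will be based on the treatment effects tested in the initial models described for CRCTs with pre-planned covariates".

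Earlier IDH appears in Section 11.4 only in other roles:

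- Instability in the previous session is a candidate mediator.
- Recent IDH is a candidate predictor in the Aim 2 models.
- The third secondary analysis is labelled as before versus after the intervention, but the periods it describes are the 24-week intervention phase and the 12-week maintenance phase.
- A covariate found unbalanced between arms may be added in a secondary model, of which the plan says: "because it will use data-driven covariate decisions that are subject to analysis bias, it will be interpreted with caution".

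On the outcome window, Aim 1 in Section 3.1 refers to "dialysis session stability over an intervention period of 24 weeks and a post-intervention follow-up period of 12 weeks". Section 11.4 says: "This outcome will be collected through digital records for all HD sessions of all patients at each facility during the study period". It does not say that baseline sessions are left out of the primary proportion.

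**The concern.** With 20 facilities, the precision of each main effect depends mainly on how much facilities differ from one another. A facility's own earlier IDH rate is the natural covariate for that component, and here it needs no new data. If facility IDH rates persist over time, leaving the baseline rate out discards precision that would be costly to buy with more facilities.

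The choice has to be made in advance. As the plan stands, baseline IDH could enter the Aim 1 treatment comparison only through the imbalance-driven model, which the plan itself treats with caution.

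The outcome window matters as well. Baseline can serve as a covariate only if baseline sessions are not also counted in the outcome.

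**Working it through.** **Inputs (Section 11.2):** 10 versus 10 facilities per main effect, 60 patients per facility, ICC 0.10, SD 0.08 to 0.10, alpha 0.05. Sidedness is not stated for Aim 1. Two-sided reproduces Table 5 and is stated for the secondary outcomes. The correlation r between baseline and later facility IDH is not in the documents; it is an assumption, varied below.

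**1. Table 5 as printed.** Design effect = 1 + 59 × 0.10 = 6.9. SE = √(2 × SD² × 6.9/600) = 0.01213 (SD 0.08) or 0.01517 (SD 0.10). The ratios D/SE are:

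- 0.034/0.01213 = 2.802
- 0.034/0.01517 = 2.242
- 0.040/0.01213 = 3.297
- 0.043/0.01517 = 2.835

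Power = Φ(D/SE − 1.96) = 80.0, 61.1, 90.9 and 80.9%, against 80, 61, 91 and 81% in the plan. Table 5 is reproduced, and it takes no credit for baseline.

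**2. Where the variance lies.** In units of SD², a facility mean has variance 0.10 + 0.90/60 = 0.115. The between-facility share is 0.10/0.115 = 87%.

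**3. Power with and without baseline.** The model is a facility-level 2×2 with main effects only. Residual df are 20 − 3 = 17 unadjusted and 16 with one facility-level covariate. Adjusted power uses a noncentral t on 16 df with noncentrality (D/SE) × √(B/(1 − r²)), averaged over B ~ Beta(8.5, 0.5). B carries chance baseline imbalance with the slope estimated. The mean of 1/B is 16/15, a variance cost of 6.7%.

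| D / SD | Unadjusted | r=0 | r=0.3 | r=0.5 | r=0.7 |
|---|---|---|---|---|---|
| 0.034 / 0.08 | 75.2% | 72.3% | 76.2% | 83.7% | 94.5% |
| 0.034 / 0.10 | 56.1% | 53.4% | 57.3% | 65.5% | 81.5% |
| 0.040 / 0.08 | 87.4% | 85.0% | 88.1% | 93.2% | 98.6% |
| 0.043 / 0.10 | 76.2% | 73.3% | 77.2% | 84.5% | 94.9% |

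A simulation of the first, second and fourth rows (200,000 runs per setting) agrees within 0.4 points, with type I error 4.9 to 5.0%.

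**4. Break-even.** On variance, (1 − r²) × 16/15 = 1 gives r = √(1/16) = 0.25. On power, r is 0.254 to 0.265 across the four cells; on confidence interval width it is 0.267. If none of r came from individual patients' persistence, r = 0.25 would need a facility effect correlated over time at 0.25/0.87 ≈ 0.29.

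**5. What r buys.** The three cells below 80% unadjusted reach it at r of about 0.41 (0.034/0.08), 0.69 (0.034/0.10) and 0.39 (0.043/0.10). The difference detectable with 80% power is:

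| SD | Unadjusted | r=0 | r=0.5 |
|---|---|---|---|
| 0.08 | 0.036 | 0.037 | 0.032 |
| 0.10 | 0.045 | 0.047 | 0.040 |

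**6. Patients without their own baseline.** Assume the 15 to 20% turnover in Section 5.4.1 is spread evenly over 48 weeks, with three sessions a week, so that 60 sessions take 20 weeks.

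- Intervention-only window: entrants in weeks 1 to 4 can still qualify, 4/48 × (15 to 20%) = 1.3 to 1.7%.
- Intervention plus follow-up: entrants in weeks 1 to 16 can qualify, 16/48 × (15 to 20%) = 5.0 to 6.7%. Week 16 is also the enrollment cut-off (24 − 8).
- Partial baseline, joining during the 12 baseline weeks: 12/48 × (15 to 20%) = 3.8 to 5.0%.

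**The case against.** The strongest reply is that this is an optional refinement. Validity is intact, and the gain rests on a correlation the documents never give. The relevant r is also what remains after a long covariate list, so raw facility persistence overstates it. All of that stands, and at r=0.3 the gain is only about one point. But the listed covariates describe patients and sessions, while Sections 2.1.3 and 2.1.4 report wide facility variation after adjustment for patient characteristics (odds ratios 0.608 to 1.468). The loss at r=0 is at most 2.9 points, against gains of 5.8 to 9.4 points at r=0.5.

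Other points have partial force:

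- **Degrees of freedom.** Part of the shortfall from 80% comes from using a t reference where Table 5 uses the normal; by the plan's method three of four cells reach 80%. The comparison with and without baseline uses t on both sides, so it is not affected.
- **Other routes for earlier IDH.** The Aim 2 models may test recent IDH, and the quality-of-life analysis already uses a pre-intervention survey. Neither puts the baseline IDH rate into the primary model. Treatment history is undefined, but nothing shows that it includes IDH.
- **Baseline timing.** In Table 2, data for Groups 3 and 4 start on July 1, 2023, while enrollment runs from October 2023 to January 2024. The baseline window therefore needs a definition tied to each facility's intervention start.
- **A second covariate.** Only the facility rate was evaluated. The patient's own baseline acts mainly on the within-facility part, 0.015 of 0.115, or 13%.
- **Who holds the records.** Section 16 names a funder as sponsor. Historical facility data sit with the dialysis organization, so checking r needs an extraction.

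**Conclusion.** The concern holds. The omission of baseline IDH from the pre-planned covariates is plain in the text; the benefit of including it is conditional. Across the four Table 5 cells, adjustment changes power by −2.4 to −2.9 points at r=0, about +1 at r=0.3, +5.8 to +9.4 at r=0.5 and +11 to +25 at r=0.7.

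This rests on equal-sized facilities, a mixed model that behaves like an analysis of facility means, the plan's ICC and SDs, and r read as the partial correlation after the other covariates. It is a matter of precision, not bias, provided the primary proportion is built from post-baseline sessions only. The plan should say so, because counting baseline sessions would dilute the effect, which is a separate fault.

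**What to change.** 1. State that baseline-period sessions are excluded from the primary proportion. Keep the post-baseline window in line with Aim 1 (24-week intervention and 12-week follow-up) unless the study team states otherwise. Define the 12 baseline weeks relative to each facility's intervention start.
2. Pre-specify the facility's 12-week baseline IDH rate as a covariate in the primary linear mixed model. Add the patient's own baseline proportion where available, with a stated rule for missing or partial baseline.
3. Use small-sample facility-level degrees of freedom for that model, for example Kenward-Roger.
4. Do the same for Aim 2 outcomes that have baseline data and do not already use it.

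Before fixing this, ask the dialysis organization for the correlation between 12-week and later IDH rates in its historical facility records. If it is clearly below about 0.25, the adjustment is not worthwhile.

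The cost is SAP wording plus that extraction; the trial data are already collected. The statistical cost is about 3 points of power if r=0. The missing-baseline rule would apply to about 1 to 2% of patients with an intervention-only window, or 5 to 7% with follow-up included. A further 4 to 5% would have partial baseline.
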